
Rationale and Purpose: In December 2019, a group of pneumonia cases was reported at a wholesale seafood market in Wuhan in the Hubei province of China. The disease, which has subsequently become known as COVID-19, was found to be caused by a previously unknown coronavirus since named severe acute respiratory syndrome coronavirus 2 (SARS-CoV-2). The first detected case of COVID-19 in South Africa was on 5th March 2020. The global and local pandemic that followed the initial outbreak has already resulted in a significant number of cases and deaths, as well as major and long-term economic, social and health sector damage. In countries that have already been severely affected, cross-sectional screening of the general population indicates that we are far from reaching “herd immunity” in those populations. There is therefore an urgent and unmet need for identification of therapies for treating COVID-19 disease and vaccines for preventing the disease. These interventions are essential to reducing morbidity and mortality and returning to a form of social and economic normalcy.
 
Human adenovirus type 5 (hAd5) is an attractive vector for vaccine development against COVID-19 because it can be readily produced at scale and has a history of safe clinical use in a vaccine setting. However, the utility of first-generation hAd5 vectors is increasingly constrained due to widespread prevalence of adenoviral (i.e. vector) immunity in the general population. A phase 1 trial of an Ad5 candidate vaccine against SARS-CoV-2 in Wuhan has already demonstrated that there is a negative impact on immunogenicity in those with high Ad5 neutralising antibodies at baseline.
 
The prior demonstration of an increased risk for HIV-1 acquisition in men who received a hAd5 vectored HIV vaccine, thought to be related to hAd5 vector induced immune responses, also needs to be considered when developing and testing a vaccine that needs inclusion of high HIV prevalence settings, such as a COVID-19 vaccine.
 
To address the urgent need for a scalable, safe vaccine that can overcome the limitations of first-generation hAd5 vaccines a 2nd generation oncology hAd5 platform has been leveraged to

create a vaccine containing SARS-CoV-2 spike (S) and nucleocapsid(N) antigens. The 2nd generation hAd5 platform has already demonstrated safety and efficacy in 125 patients in 13 clinical trials including at the National Cancer Institute.

To avoid the adenovirus (Ad) immunization barrier for first generation Ad5 [E1-, E3-] vectors, the 2nd-generation hAd5 vector has two additional deletions in the E2b region, removing the DNA polymerase and the preterminal protein genes (E1-, E2b-, E3-). Deletion of the E2b region confers advantageous immune properties on the novel hAd5 vectors, eliciting potent immune responses to inserted antigens while minimizing the immune responses to Ad5 proteins. Thus, the hAd5 [E1-, E2b-, E3-] vector overcomes limitations of early generation vectors, as it permits the immunization of people who have been previously exposed to Ad5. Further, overcoming this vector induced immune responses thought to contribute to increased HIV acquisition risk makes the candidate feasible for testing in high HIV prevalence settings. We believe that hAd5 [E1-, E2b-, E3-] vectors are likely superior to Ad5 [E1-, E3-] vectors in immunogenicity and safety and are the best platform to develop a COVID-19 vaccine in a rapid and efficient manner.

To date, the majority of vaccine strategies in development involve developing immunogenicity against S protein. However, recent evidence in patients who recovered from COVID-19 demonstrates Th1 immunity generated against N protein ([Grifoni 2020](#)). A second report by Grifoni et al. further confirmed that in the predictive bioinformatics model, T and B cell epitopes were highest for both S and N ([Grifoni 2020b](#)).

The hAd5 vector with E1/E2b/E3 deletions has been engineered to express optimized forms of SARS-CoV-2 S and N proteins. The vaccine product, known as hAd5-S-Fusion+N-ETSD, encodes for an optimized S protein (S-Fusion) to enhance stability and cell surface expression of the critical Receptor Binding Domain(RBD); and N protein with an enhanced T-cell stimulation domain (N-ETSD) to enhance cell-mediated immunity. In vitro experiments showed that hAd5-S-Fusion+N-ETSD demonstrates enhanced expression and exposure of the S protein RBD relative to S alone. In an *in vivo* mouse model, hAd5-S-Fusion+N-ETSD was shown to stimulate antibody production and cell-mediated immunity following vaccination. IgG isotyping analysis demonstrated that hAd5-S-Fusion+N-ETSD also induced Th1 response. Sera from mice vaccinated with hAd5-S-Fusion+N-ETSD demonstrated robust neutralizing activity when tested in a live virus neutralization assay and in a surrogate neutralization assay probing RBD binding to receptor. Furthermore, on the basis of the recent clinical data from patients recovered from COVID-19 reported by Grifoni et al, as well as the corroborating preclinical data that the N protein induces long lasting CD4+ and Th1 cell-mediated immunity, it is hypothesized that this combination of S-Fusion+N-ETSD could provide long-lasting immunity beyond short term neutralizing antibodies.

Thus, it is the purpose of this trial to confirm the potential that by combining S with N, long-term cell-mediated immunity with a Th1 phenotype can be induced. The potential exists for this combination vaccine to serve as a long-term “universal” COVID-19 vaccine in light of mutations undergoing in S and the finding that the structural N protein is highly conserved in the coronavirus family. The trial is designed to assess the safety, reactogenicity and immunogenicity of hAd5-S-Fusion+N-ETSD and identify an optimal dose for future clinical studies.

In cohorts 3, 4, 5, and 6 of the study only participants who are SARS-CoV-2 antibody serology positive will be enrolled to evaluate boosting of pre-existing SARS-CoV-2 immune responses and compare the effect of route of administration on the efficacy (and magnitude thereof), reactogenicity and safety of the boosting effect. Our objective is to evaluate this novel vaccine candidate for its potential to boost pre-existing immune responses, where it might well have an important application in future to increase the magnitude and breadth of pre-existing immune responses to SARS-CoV-2 (due to either prior infection or prior vaccination) and provide enhanced, more durable immunity and protection against variants. We will test different routes of administration of the booster – that being subcutaneous, sublingual, subcutaneous plus sublingual, and intranasal. The sublingual administration involves use of the same study product but administered by syringe sublingually. The intranasal also involves the same study product with a delivery device designed for intranasal delivery through atomisation.

Study Objectives	Study Endpoints

Primary
 
Safety: To determine the safety and reactogenicity of the hAd5-S-Fusion+N-ETSD vaccine at two dose levels for subcutaneous administration, and for sublingual and intranasal dosing.
 
Immunogenicity: To determine immunogenicity of hAd5-S-Fusion+N-ETSD as determined by changes in humoral response.
	
Safety:
 
 • Incidence of MAAEs and SAEs through 1 week post final vaccine administration • Incidence and severity of solicited local reactogenicity AEs through 1 week post final vaccine administration • Incidence and severity of solicited systemic reactogenicity AEs through 1 week post final vaccine administration • Incidence and severity of unsolicited AEs through 1 week post final vaccine administration • Incidence of MAAEs and SAEs through 30 days and 6 months post final vaccine administration • Incidence and severity of unsolicited AEs through 30 days and 6 months post final vaccine administration • Incidence of abnormal changes of laboratory safety examinations • Changes in vital signs 
Immunogenicity: Timing per Schedule of Events
 
 • GMFR in IgG titer to SARS-CoV-2 S, RBD and N. • GMT of S-specific, RBD-specific, and N-specific antibodies against 2019 novel coronavirus tested by ELISA in serum . • Percentage of participants who seroconverted (defined as 4-fold change in antibody titer relative to baseline) . • GMFR in neutralizing antibody .

	
 • GMT of neutralizing antibody . • Seroconversion rate of neutralizing antibody (defined as 4-fold change in antibody titer relative to baseline) .
Secondary	
Safety: 
 • Ascertainment of HIV infections in vaccine recipients through 12 months post final vaccine administration 	Safety: 
 • New HIV infections in vaccine recipients by either two locally approved rapid antibody tests or by ELISA, conducted per Schedule of Events through 12 months post final vaccine administration
Exploratory	
Immunogenicity: To determine cellular and mucosal immunogenicity of hAd5-S-Fusion+N-ETSD. To assess for any induction or enhancement of Ad5 immune response by the Ad5 vector in hAd5-S-Fusion+N-ETSD.	Immunogenicity: Timing per Schedule of Events 
 • T cell activity against SARS-CoV-2 S, RBD and N protein • Mucosal Immunogenicity as assessed by GMT of IgA antibody levels to SARS CoV-2 S protein, RBD and N protein • T cell activity and IgG titres against Ad5, comparing baseline to day 29 and day 181 and 202(in cohorts 3, 4, 5, 6 and cohorts 1 and 2 respectively)

Study Design:

This is a phase 1b, open-label study in adult healthy participants. This clinical trial is designed to assess the safety, reactogenicity, and immunogenicity of the hAd5-S-Fusion+N-ETSD vaccine and select a dose for future studies. The hAd5-S-Fusion+N-ETSD vaccine is a hAd5 [E1-, E2b-, E3-] vector-based targeting vaccine encoding the SARS-CoV-2 S and N proteins. The hAd5-S-Fusion+N-ETSD vaccine is designed to induce both humoral and cellular responses even in individuals with pre-existing adenoviral immunity. Thus, the potential exists for the hAd5-S-Fusion+N-ETSD to induce SARS-CoV-2 immunity and prevent or lessen the health impact of COVID-19 infection in healthy participants. Up to 60 healthy participants will be divided into 6 cohorts:

Study Cohorts, Dosing Schedules, Mode of Administration and Dose of hAd5-S-Fusion+N-ETSD

Cohort	Number of participants	Dosing Schedule	Mode of Administration	Dose
1	10	Day 1	SC	5×10^{10} VP
		Day 22	SC	5×10^{10} VP
2	10	Day 1	SC	1×10^{11} VP*
		Day 22	SC	1×10^{11} VP*
3	10	Day 1	SC	1×10^{11} VP*
4	10	Day 1	SL	1×10^{11} VP
5	10	Day 1	SC	1×10^{11} VP*
			and SL	1×10^{11} VP
6	10	Day 1	IN	2×10^{10} VP into each nostril**

SC= subcutaneous; SL= sublingual; IN= intranasal; VP= viral particles; * In the event of safety concerns participants will be dosed at 5×10^{10} VP/dose; ** Total IN dose is given is 4×10^{10} VP as vaccine will be administered into both nostrils

Cohort 1-2 enrolled participants who were SARS-CoV-2 antibody serology negative. For cohorts 3-6, only participants who are SARS-CoV-2 antibody serology positive will be enrolled to evaluate boosting of pre-existing SARS-CoV-2 immune responses and compare the effect of route of administration on the efficacy (and magnitude thereof), reactogenicity and safety of the boosting effect.

The Safety Review Committee (SRC), including at least one qualified infectious disease physician independent of the Sponsor and trial reviews safety data.

The SRC will first assess safety when all Cohort 1 participants have completed the toxicity assessment period (defined as 7 days after first vaccine dose, i.e. study day 8). In the absence of safety concerns, enrolment in Cohort 2 will be initiated. The SRC will similarly also assess safety when each of Cohort 2, 3, 4 and 5 participants have completed the toxicity assessment period (defined as 7 days after first vaccine dose, i.e. study day 8). In the absence of safety concerns, enrolment in Cohort 3, 4, 5 and 6 respectively will proceed. Cohorts 3 and 5 will be dosed at 1×10^{11} VP/dose for SC administrations. If safety concerns are identified at the higher dose of 1×10^{11} VP/dose, Cohort 3 and 5 participants will be dosed at 5×10^{10} VP/dose for SC administrations.

All participants will have follow up study visits for the collection of safety, reactogenicity, and/or immunogenicity data at 7 and 14 days after each vaccine dose, 30 days after the last dose, and at 90, 180 and 365 days following the last dose. Additional follow up for safety information will occur via telephone contact as noted in the Schedule of Events.

Safety will be assessed for all participants and will include monitoring of vital signs, and incidence and severity of AEs. Blood samples will be collected for haematology and chemistry analyses and urine samples will be collected for urinalysis. Toxicities will be graded using the Guidance for Industry: Toxicity Grading Scale for Healthy Adult and Adolescent Volunteers Enrolled in Preventive Vaccine Clinical Trials (2007). Solicited local and systemic AEs and unsolicited AEs will be collected using diary cards for 7 days following any dose of vaccine.

Solicited local AEs to be assessed include

Subcutaneous dosing includes injection site:

- Pain,
- Itching,
- Induration,
- Swelling,
- Erythema.

Sublingual dosing include:

- Oral burning,
- Oral swelling,
- Difficulty swallowing,
- Difficulty breathing.

Intranasal dosing include:

- Nasal congestion and coryza
- Epistaxis,
- Pain in the nose,

Solicited systemic AEs to be assessed include chills, fever, nausea, vomiting, diarrhoea, headache, fatigue, and myalgia. Safety visits and telephone calls will occur at scheduled times until 6 months after the last vaccine dose, and will be used to collect unsolicited AEs occurring since the last study contact, as well as any solicited AEs continuing beyond the 7-day period after vaccination.

Immunogenicity analyses will be conducted by collecting serum, peripheral blood mononuclear cell (PBMC) and saliva samples from individual patients before and after vaccinations to test for humoral- and cell- mediated immune responses. Immunogenicity assessments will be conducted for up to 1 year after the last vaccine dose.

Enrolment (planned):

Up to 60 participants will be enrolled in this study.

Eligibility Criteria:

Inclusion Criteria:

1. Adults, age 18 – 50 years, inclusive, at time of first study vaccination.
2. SARS-CoV-2 antibody positive for cohorts 3, 4, 5, and 6 (by a locally approved serology assay)
3. Able to understand and provide a signed informed consent that fulfils the relevant Institutional Review Board (IRB) or Independent Ethics Committee (IEC) guidelines.
4. Agrees to the collection of biospecimens (e.g., nasopharyngeal [NP] swabs) and venous blood per protocol.
5. Ability to attend required study visits and return for adequate follow-up, as required by this protocol.
6. Body mass index(BMI) <30.00kg/m²
7. Temperature < 38°C on day of first study vaccination.
8. Good general health as shown by medical history, physical exam, and screening laboratory tests
9. Screen negative for Tuberculosis per local screening guidelines
10. Male participants should all be at low risk of HIV acquisition based on pre-specified, validated criteria i.e. answering YES to any of the following questions:
 - a. Are you sexually abstinent?
 - b. Are you in a mutually monogamous relationship with a known HIV-uninfected partner?
 - c. Have you had only one partner in the preceding 12 months who is believed to be HIV-uninfected and with whom condoms were used regularly?

Laboratory Inclusion Values/ Results:

11. Alanine aminotransferase (ALT) <1.1 times the upper limit of normal
12. Serum Creatinine <80 umol/L in females and <106 umol/L in males
13. Haemoglobin >12.0g/dL in females and >13.5g/dL in males
14. Platelets >150 x 10⁹/L in all participants
15. No serological evidence of chronic infection with Hepatitis B (hepatitis B surface antigen (HepBSAg) negative by a locally approved assay) done during the screening period
16. No serological evidence of chronic infection with Hepatitis C (hepatitis C antibody(anti-HCV) negative by a locally approved assay) done during the screening period
17. Negative for SARS-CoV-2 (PCR test) on NP swab(or other appropriate respiratory specimen) within 3 days (calendar days) prior to the first study vaccination

18. A negative serum or urine pregnancy test during screening and on the day of and prior to each dose must be documented before the vaccine is administered to a female participant of childbearing potential.
19. Negative for HIV-1 and -2 on blood test (by either 2 rapid tests or an ELISA, both must be locally approved assays) done during the screening period.

Reproductive Status:

20. Female participants of childbearing potential must agree to consistently practice effective contraception for sexual activity that may lead to pregnancy while on study and until at least 30 days after the last dose of the study vaccine. Effective contraception for female participants includes:

21. Intrauterine device (IUD), or
22. Hormonal contraception (oral/ injectable/ implant/ transdermal etc.)

Or;

23. Non-sterile male participants must agree to use a condom or spermicide while on study until at least 30 days after the last dose of the study vaccine.

Or;

24. Participant must not be of reproductive potential or sterile (as verified by medical records), such as:

- Having been diagnosed with menopause (with no menses for 1 year)
- Having undergone hysterectomy, bilateral oophorectomy or orchidectomy
- Having undergone surgical sterilization (e.g., vasectomy, tubal ligation)

[figure not shown]
Exclusion Criteria:

1. Serious adverse reaction to any vaccine, any unrelated medication or any component of the investigational vaccine, including a history of anaphylaxis and symptoms of a severe allergic reaction and history of allergies in the past.
2. Pregnant or breastfeeding women.
3. Live in a nursing home or long-term care facility.
4. Chronic lung disease or moderate to severe asthma
5. Bone marrow or organ transplant recipient
6. Diabetes.
7. Chronic kidney disease requiring dialysis.
8. Liver disease.
9. Any disease associated with acute fever, or any infection.
10. Chronic hepatitis B or hepatitis C infection.


11. HIV positive or other acquired or hereditary immunodeficiency.
 
12. Serious cardiovascular diseases, such as arrhythmia, conduction block, previous myocardial infarction, uncontrolled severe hypertension
 
13. History of hereditary, idiopathic or acquired angioedema.
 
14. Urticaria 12 months prior to screening.
 
15. No spleen or functional asplenia.
 
16. Platelet disorder or other bleeding disorder that may cause injection contraindication.
 
17. Chronic use (more than 14 continuous days) of any medications that may be associated with impaired immune responsiveness including, but not limited to, systemic corticosteroids exceeding 10 mg/day of prednisone equivalent, allergy injections, immunoglobulin, interferon, or immunomodulators. The use of low dose topical, ophthalmic, inhaled and intranasal steroid preparations will be permitted.
 
18. Prior administration of blood products within 120 days before first study vaccination.
 
19. Prior administration of other research medicines or investigational product within 30 days before first study vaccination.
 
20. Prior administration of attenuated vaccine within 30 days before first study vaccination.
 
21. Prior administration of inactivated vaccine within 14 days before first study vaccination.
 
22. Prior administration of SARS-CoV-2 vaccine or likely to receive SARS-CoV-2 vaccination within the upcoming 28 days
 
23. Current treatment with investigational agents for prophylaxis of COVID-19.
 
24. Have a household contact that has been diagnosed with COVID-19 within 14 days before first study vaccination.
 
25. Current anti-tuberculosis prophylaxis or therapy.
 
26. Currently receiving treatment for cancer or history of cancer in the last five years (except basal cell carcinoma of the skin and cervical carcinoma in situ).
 
27. According to the judgement of the investigator any medical, psychiatric, psychological, social, occupational or other conditions that could affect the participants ability to sign informed consent, provide safety assessment data or comply with the requirements of the study protocol.
 
28. Assessed by the Investigator to be unable or unwilling to comply with the requirements of the protocol.
	
Duration of Treatment: Each participant will receive hAd5-S-Fusion+N-ETSD on Day 1. Cohorts 1 & 2 receive a second dose of hAd5-S-Fusion+N-ETSD at Day 22.

--	--


Duration of Follow-up:
 
Participants who receive study treatment will be followed by a health care professional until either death (by any cause) or for a minimum of 12 months past administration of last administration of hAd5-S-Fusion+N-ETSD.
	
Reference Therapy, Dosage, and Mode of Administration:
 
Not applicable


Evaluation of Endpoints:
 
Safety: Safety endpoints include assessments of treatment-emergent MAAEs, SAEs, solicited local and systemic reactogenicity AEs, unsolicited AEs, safety laboratory tests, HIV testing and vital signs. Toxicities will be graded using the Guidance for Industry: Toxicity Grading Scale for Healthy Adult and Adolescent Volunteers Enrolled in Preventive Vaccine Clinical Trials (2007).
 
Immunogenicity: GMT of S-specific and N specific antibodies against 2019 novel coronavirus, GMT of neutralizing antibody, and GMT of IgA antibody levels will be evaluated. T cell activity against SARS-CoV-2 S, RBD and N protein will be measured by standard immune assays. Humoral and cellular immunity against the Ad5 vector will be measured at baseline, day 29 and day 181 and 202 (in cohorts 3, 4, 5, 6 and cohorts 1 and 2 respectively) to assess for any induction or enhancement of Ad5 immune responses.
	
Statistical Methods:
 
The purpose of this study is to determine the safety, reactogenicity, and immunogenicity of hAd5-S-Fusion+N-ETSD and select an optimal dose and formulation for future studies. Descriptive statistics will be presented for all study endpoints by individual cohort, pooled by dose level, and for all cohorts combined.
 
Safety will be assessed by the incidence of treatment-emergent MAAEs, SAEs, and solicited local and systemic reactogenicity AEs, and unsolicited AEs for the time period of interest, overall and by grade using the Guidance for Industry: Toxicity Grading Scale for Healthy Adult and Adolescent Volunteers Enrolled in Preventive Vaccine Clinical Trials (2007). Clinically significant changes in safety laboratory tests and vital signs also will be summarized. As suggested by the Ad5 literature and expert opinion, participants will be monitored for incident HIV infection during the follow up period .
 
Immunology analyses will be used to provide an assessment of immune responses. GMFRs and GMTs and their associated 95% confidence intervals (CIs) will be computed by exponentiation of the corresponding log-transformed means and 95% CIs. The percentage of participants who seroconverted (as defined as 4-fold change in antibody titer relative to baseline) and 95% Clopper-Pearson CI will be summarized. Neutralizing antibody levels and CD8+ and CD4+ T-Cell activity also will be summarized.

Figure 1: Study Schema

* In the event of safety concerns participants will be dosed at 5×10^{10} VP/dose

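### Long-term Th1 immunity induced by combining S with N is not demonstrable as specified, and the pooled immunogenicity summaries mix induction with boosting

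*Combined protocol and SAP*

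**What the plan says.** The closing paragraph of the synopsis section Rationale and Purpose gives the aim as to "confirm the potential that by combining S with N, long-term cell-mediated immunity with a Th1 phenotype can be induced". The same paragraph continues: "The trial is designed to assess the safety, reactogenicity and immunogenicity of hAd5-S-Fusion+N-ETSD and identify an optimal dose for future clinical studies".

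In the objectives and endpoints table, the primary immunogenicity objective is humoral: "To determine immunogenicity of hAd5-S-Fusion+N-ETSD as determined by changes in humoral response". Cellular immunity is exploratory: "To determine cellular and mucosal immunogenicity of hAd5-S-Fusion+N-ETSD", with the endpoint "T cell activity against SARS-CoV-2 S, RBD and N protein". Under Evaluation of Endpoints this activity "will be measured by standard immune assays". Statistical Methods adds: "Neutralizing antibody levels and CD8+ and CD4+ T-Cell activity also will be summarized".

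Study Design gives six cohorts of 10, all on hAd5-S-Fusion+N-ETSD. Cohorts 1-2 are seronegative and receive two doses. Cohorts 3-6 are seropositive, receive vaccine on Day 1 only, and serve a declared boosting aim. Reference therapy is not applicable.

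Statistical Methods presents every endpoint three ways: for each cohort, in pools formed by dose level, and over all cohorts together.

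**The concern.** The purpose sentence has three parts that the design must support: a Th1 phenotype, a response that is induced, and a response that arises from putting S and N together. The endpoints and analysis sets do not support them as written.

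- **Th1.** The supplied text names no cytokine, Th1/Th2 measure, IgG subclass or T-cell responder rule for any endpoint. CD4+ activity alone does not establish Th1. The only Th1 evidence the synopsis gives for this vaccine is from mice, by IgG isotyping, and isotyping is not an endpoint here.
- **Induced.** Exclusion criterion 22 bars earlier SARS-CoV-2 vaccination, so seropositivity in Cohorts 3-6 should reflect infection. The Rationale itself says that "recent evidence in patients who recovered from COVID-19 demonstrates Th1 immunity generated against N protein". A late N-specific Th1 response in those cohorts is therefore not evidence that the vaccine induced it.
- **By the combination.** No cohort receives a product without N.

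At stake is what the trial may conclude. A pooled table of T-cell or antibody responses could be read as evidence of induction when most of the people in it had existing responses that were being boosted.

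**Working it through.** **Inputs.** Cohort sizes, doses and serostatus come from the cohort table and text in Study Design. The pooling rule comes from Statistical Methods. Visit timing comes from the Schedule of Events, using the days-after-dose rows. The documents give no power or precision basis for the sample size, so only the total can be reproduced.

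**1. Cohort totals.** 6 × 10 = 60, which matches the planned maximum. Seropositive: 4 × 10 = 40, and 40/60 = 66.7%. Seronegative: 2 × 10 = 20.

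**2. What each pool contains, if full dosing proceeds.**

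| Summary | Cohorts | n | Seropositive |
|---|---|---|---|
| Each cohort | one | 10 | 0% or 100% |
| 1×10^11 VP pool | 2, 3, 4 | 30 | 20/30 = 67% |
| All cohorts | 1-6 | 60 | 40/60 = 67% |

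The plan does not say how Cohort 5, which receives 1×10^11 VP by each of two routes, enters the dose-level pools. If it joined the 1×10^11 VP pool, the seropositive share would be 30/40 = 75%. Number of doses also differs within that pool: two in Cohort 2, one in Cohorts 3 and 4. No planned summary shows Cohorts 1-2 together as a group of 20.

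**3. What a pooled figure means.** The all-cohort responder proportion is (20/60) × p(seronegative) + (40/60) × p(seropositive). Illustration with assumed counts: 16/20 = 80% and 20/40 = 50% give 36/60 = 60%, which describes neither group. The same 1:2 weighting applies to mean log fold-rise, and so to the pooled GMFR.

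**4. Precision of an induction statement (Clopper-Pearson 95% CI, the plan's own method for seroconversion).** The responder counts are assumptions.

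- 8/10: 44% to 97.5%
- 16/20: 56% to 94%
- 20/20: 83% to 100%

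Induction in Cohorts 1-2 can be estimated, with low precision.

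**5. Would an S-only arm help?** The formula is n per arm = [1.96√(2p̄(1−p̄)) + 0.842√(p1(1−p1) + p2(1−p2))]² / (p1−p2)², for two-sided 5% and 80% power. The rates are assumptions.

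| Responders, S-only vs S+N | n per arm | Power at 10 per arm | Power at 20 per arm |
|---|---|---|---|
| 50% vs 90% | 20 | 50% | 81% |
| 50% vs 80% | 39 | 28% | 51% |
| 60% vs 80% | 82 | 16% | 28% |

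For the first row, p̄ = 0.70: (1.270 + 0.491)² / 0.16 = 19.4, rounded up to 20. At this trial's cohort sizes, such an arm would detect only a very large contribution of N.

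**The case against.** The strongest reply is that one sentence of rationale is being treated as the operative aim. It speaks only of confirming a potential, the next sentence gives the aim as safety, immunogenicity and dose, and Statistical Methods says much the same. No objective or planned analysis tests whether N adds anything to S. Much of the remedy already exists: T-cell activity is listed by antigen, blood is taken before dosing and up to a year after the last dose, each cohort has a single serostatus, and Cohorts 3-6 are described as boosting.

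Most of this stands, and it rules out several stronger readings that a reader might infer:

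- *The purpose cannot be met.* Not supported. Confirming a potential needs no comparative claim, and 20 seronegative participants are followed from their own baseline.
- *No endpoint measures Th1.* The documents show only that none specifies it. Standard immune assays could include a Th1 cytokine, and assay detail may lie outside the supplied text.
- *Two-thirds of participants are already immune, so enrolling them is a design fault.* The criterion is antibody seropositivity, and those cohorts serve a declared objective.
- *The lack of an S-only arm is a flaw to repair.* A descriptive phase 1b study does not need one for a narrower statement.

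The reply does not answer the pooling or the wording. By-cohort tables do not stop the pooled tables from mixing serostatus, and nothing in the design supports crediting the combination.

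**Conclusion.** The point holds as a mismatch between the stated purpose and what the endpoints and summaries can show. No Th1 readout is specified in the supplied text, none of the six cohorts lacks N, and new induction can be described in at most 20 of 60 participants. The all-cohort pool is 67% seropositive, as is the 1×10^11 VP pool formed from Cohorts 2-4, so both mix induction with boosting.

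This assumes full enrolment, that the dose concession for safety concerns is not used, and that seropositivity reflects earlier infection. The responder counts and rates in the working are illustrations. The safety conclusions and the sample size are not affected. The pooled primary antibody summaries are, because the pooling rule covers every endpoint.

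**What to change.** 1. **Summaries.** For T-cell and other immunogenicity endpoints, keep the by-cohort tables and replace the dose-level and all-cohort pools with summaries by baseline serostatus: Cohorts 1-2 and Cohorts 3-6. Base any statement about induction or durability on paired change from Day 1 in Cohorts 1-2, at the scheduled visits 30, 180 and 365 days after the last dose. Flag participants with intercurrent infection, using the PCR and COVID-19 history already scheduled. Do not exclude those with a Day 1 T-cell response; paired change allows for baseline, and exclusion would shrink the 20 further. Describe Cohorts 3-6 as change in existing responses.
2. **Readout.** Report CD4+ responses to S and to N with a Th1 and a Th2 cytokine readout on PBMC already collected, as far as sample volume allows (the documents give no volumes). State this before the data are examined, since the trial is open-label.
3. **Purpose.** Reword it to describe S- and N-specific T-cell responses after the vaccine, without attributing them to combining S with N.

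No extra participants, visits or S-only arm are needed. The cost is text changes, possible added assay work, and an induction claim from 20 participants with wide intervals.
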